7 REGISTRATION PROCEDURES

7.1 CUMC Research Participant Registration

Confirm eligibility as defined in the section entitled Criteria for Participant Eligibility.

Obtain informed consent, by following procedures defined in section entitled Informed Consent Procedures, along with applicable institutional policies and federal regulations.

Only Investigators/Research personnel properly trained and delegated to consent participants for this protocol will participate in the consenting process. Furthermore, properly delegated/trained Physician Investigators (e.g., MD, MD PhD) are required to sign/verify a protocol specific Eligibility Checklist for each participant enrolled on the study, in addition to providing the relevant source documentation confirming participant eligibility.

All participants must be centrally registered through the Central Registration Office within Herbert Irving Comprehensive Cancer Center at CUMC prior to initiation of study treatment.

Registration hours are available Monday through Friday from 9:00am – 5:00pm EST (excluding holidays and weekends). Same day participant registrations (and after hour registrations) will be accommodated on a case by case basis provided that the study team has expressed all time

sensitive registration concerns/cases in a timely manner to the Central Registration Office.

CPDM Central Registration Procedures (CUMC only):

Within 48 hours of obtaining consent (excluding holidays and weekends), a completed/signed IRB approved informed consent HIPAA form, and demographics forms must be submitted to the CPDM Central Registration Office via an email to [contact] or fax to [contact], with the subject line “AAAR6354 Pending Subject Registration Request (PHI)”. Upon receipt, applicable participant information as well as a “pending eligibility” status will be entered into HICCC’s institutional database. This status will remain until further source documentation is made available to confirm overall participant eligibility. Required materials for all pending registration submissions are as follows:

- Completed/signed IRB approved/stamped Informed Consent Forms.
- The completed/signed IRB approved HIPAA Authorization form
- Completed/signed CPDM ICF checklist
- Completed/signed HICCC personal census form
- Completed/signed CPDM Demographics Note to File

In order to confirm eligibility status, Investigators/designees (e.g., study specific Clinical Research Coordinator/Research Nurse, etc.) must submit the following documentation to the Central Registration Office via email or fax:

- The completed/signed study specific Eligibility Checklist (signed by an Physician level Investigator)
- Copies of source documentation necessary for each item to be verified on the CPDM specific Eligibility Checklist, including but not limited to:
 - Copy of required laboratory test and procedure reports (e.g., hematology, serum chemistry, pregnancy test when applicable, MRI reports, CT/bone scans, etc.)
 - Copy of pathology and surgical reports
 - Copy of clinic note(s) or other appropriate medical records capturing the consent process information, along with providing source documentation of any other items needed for screening/eligibility that are not captured in other source document forms (e.g., positive investigator statements of unique eligibility items not captured via other direct source documentation, concomitant medication lists, etc.)
 - Protocol deviation/waiver approvals (if applicable)

Columbia University Medical Center
Herbert Irving Comprehensive Cancer Center
Version Date: January 30, 2024

- **Please note:** subject line of email or fax should include the following: “AAAR6354 Complete Subject Registration Request (PHI)”.

Upon receipt of the above mentioned documentation, participant eligibility information will be verified by a qualified Central Registration Registrar. If any questions arise during the review process, queries in the form of emails will be addressed to the applicable study team personnel for clarification prior to enrollment. All applicable finalized registration/eligibility information will then be entered into HICCC’s institutional CTMS database by the Central Registration Registrar. Upon completion, an official participant registration notification email will be sent to the PI/research team which will include eligibility/enrollment status, as well as participant ID information. Protocol therapy may not be initiated prior to receipt of this notification from the Central Registration Office.

All screen fail/ineligible participants, as well as participant’s who withdraw consent prior to enrollment/initiation of protocol therapy must be submitted to the Central Registration office in a manner analogous to the procedures noted above. Applicable source documentation will be required within the corresponding submissions.

8 TREATMENT PLAN

8.1 Agent Administration

Treatment will be preferentially administered on an outpatient basis. Reported adverse events and potential risks for nivolumab are described in Section 8.2. Appropriate dose modifications for nivolumab are described in Section 9. No investigational or commercial agents or therapies other than those described below may be administered with the intent to treat the participant’s malignancy.

Agent	Dose	Route	Schedule	Cycle Length
Nivolumab	240mg	IV over 30 minutes (± 7 minutes) infusion	Cycle 1-8	2 weeks (14 days)
	480mg		Cycle 9 – end of study	4 weeks (28 days)

8.1.1 Prophylactic Agent(s)

There are no prophylactic regimens required prior to administration of nivolumab.

8.2 General Concomitant Medication and Supportive Care Guidelines

Management Algorithms for Immuno-Oncology Agents

Immuno-oncology (I-O) agents are associated with AEs that can differ in severity and duration than AEs caused by other therapeutic classes. Nivolumab is considered an I-O agent in this protocol. Early recognition and management of AEs associated with I-O agents may mitigate severe toxicity. Management algorithms have been developed to assist investigators in assessing and managing the following groups of AEs:

- Gastrointestinal
- Renal
- Pulmonary
- Hepatic
- Endocrinopathy
- Skin
- Neurological

The above algorithms are found in the nivolumab Investigator Brochure and Appendix 1 of this protocol.

Treatment of Nivolumab-Related Infusion Reactions

Since nivolumab contains only human immunoglobulin protein sequences, it is unlikely to be immunogenic and induce infusion or hypersensitivity reactions. However, if such a reaction were to occur, it might manifest with fever, chills, rigors, headache, rash, pruritus, arthralgias, hypotension, hypertension, bronchospasm, or other allergic-like reactions. All Grade 3 or 4 infusion reactions should be reported within 24 hours and reported as an SAE if it meets the criteria. Infusion reactions should be graded according to National Cancer Institute (NCI) CTCAE v4.03 guidelines.

Treatment recommendations are provided below and may be modified based on local treatment standards and guidelines, as appropriate:

For Grade 1 symptoms (mild reaction; infusion interruption not indicated; intervention not indicated):

- Remain at bedside and monitor participant until recovery from symptoms. The following prophylactic premedications are recommended for future infusions: diphenhydramine 50 mg (or equivalent) and/or acetaminophen/paracetamol 325 to 1000 mg at least 30 minutes before additional nivolumab administrations.

For Grade 2 symptoms (moderate reaction required therapy or infusion interruption but responded promptly to symptomatic treatment [eg, antihistamines, non-steroidal anti inflammatory drugs, narcotics, corticosteroids, bronchodilators, IV fluids]; prophylactic medications indicated for ≤ 24 hours):

- Stop the nivolumab infusion, begin an IV infusion of normal saline, and treat the participant with diphenhydramine 50 mg IV (or equivalent) and/or acetaminophen/paracetamol 325 to 1000 mg; remain at bedside and monitor participant until resolution of symptoms. Corticosteroid and/or bronchodilator therapy may also be administered as appropriate. If the infusion is interrupted, then restart the infusion at 50% of the original infusion rate when symptoms resolve; if no further complications ensue after 30 minutes, the rate may be increased to 100% of the original infusion rate. Monitor participant closely. If symptoms recur, then no further nivolumab will be administered at that visit.
- For future infusions, the following prophylactic premedications are recommended: diphenhydramine 50 mg (or equivalent) and/or acetaminophen/paracetamol 325 to 1000 mg should be administered at least 30 minutes before nivolumab infusions. If necessary, corticosteroids (up to 25 mg of hydrocortisone or equivalent) may be used.

For Grade 3 or 4 symptoms (Grade 3: severe reaction, prolonged [ie, not rapidly responsive to symptomatic medication and/or brief interruption of infusion], recurrence of symptoms following initial improvement, hospitalization indicated for other clinical sequelae [eg, renal impairment, pulmonary infiltrates]; Grade 4: life threatening, pressor or ventilatory support indicated):

- Immediately discontinue infusion of nivolumab. Begin an IV infusion of normal saline and treat the participant as follows: Recommend bronchodilators, epinephrine 0.2 to 1 mg of a 1:1000 solution for subcutaneous administration or 0.1 to 0.25 mg of a 1:10,000 solution injected slowly for IV administration, and/or diphenhydramine 50 mg IV with methylprednisolone 100 mg IV (or equivalent), as needed. Participant should be monitored until the investigator is comfortable that the symptoms will not recur. Nivolumab will be permanently discontinued. Investigators should follow their institutional guidelines for the treatment of anaphylaxis. Remain at bedside and monitor participant until recovery of the symptoms.

In case of late-occurring hypersensitivity symptoms (eg, appearance of a localized or generalized pruritus within 1 week after treatment), symptomatic treatment may be given (eg, oral antihistamine or corticosteroids).

8.3 Duration of Therapy

In the absence of treatment delays due to adverse events, treatment may continue for 28 cycles or until one of the following criteria applies:

- Disease progression
- Intercurrent illness that prevents further administration of treatment
- Unacceptable adverse events(s)

- Participant decides to withdraw from the study
- General or specific changes in the participant's condition render the participant unacceptable for further treatment in the judgment of the investigator

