Study Product, Dose, Route, Regimen	Nivolumab (Opdivo®) 240mg IV every 2 weeks for 8 cycles. Starting with cycle 9, nivolumab 480mg IV every 4 weeks until completion of study.
Duration of administration	Up to 2 years
Reference therapy	Not applicable
Statistical Methodology	Objective response rates (partial and complete responses) will be calculated. The null hypothesis is set at an overall response rate of 10% based on historical data in subjects with recurrent high-grade gliomas with the alternative hypothesis being an overall response rate of 30%.

Protocol Schema:

Subjects with pathologically confirmed IDH mutant (grades 2, 3 or 4) gliomas with recurrent or progressive disease after treatment with alkylating agents

37 subjects with recurrent IDH mutant (grades 2, 3 or 4) glioma previously treated with alkylating agents

Nivolumab 240 mg IV
Q2W for 8 cycles

Nivolumab 480 mg IV
Q4W 2 years maximum treatment duration

Total treatment duration for 2 years or until PD, unacceptable toxicity, or withdrawal of consent. Tumor assessments every 8 weeks for up to 2 years and then per local standard of care or until progression of disease. Continuous toxicity assessments during treatment phase and for first 2 safety follow-up off-drug visits. Survival follow-up will occur every 3 months thereafter.

Contents

PROTOCOL SIGNATURE PAGE	3
1 Introduction.....	9
2 Study Objectives	9
2.1 Primary Objective	9
2.2 Secondary Objectives.....	9
2.3 Exploratory Objectives	9
3 Background	9
4 Investigational Agent.....	13
4.1 Product Development.....	13
4.2 Preclinical Data.....	13
4.3 Clinical Data	14
5 Study Design.....	18
5.1 General Design.....	18
5.2 Primary Objective	19
5.3 Secondary Objectives.....	20
5.4 Exploratory Objectives	20
5.5 Correlative Studies Background	20
5.6 Safety Assessments.....	21
5.7 Number of Participants	23
6 Participant Selection and Withdrawal.....	23
6.1 Inclusion Criteria	23
6.2 Exclusion Criteria	24
6.3 Definition of Women of Childbearing Potential.....	25
6.4 MRI Contraindication	26
6.5 Concomitant Treatments.....	26
6.6 Corticosteroids Restrictions and Precautions.....	26
6.7 Inclusion of Women and Minorities	27
6.8 Participant Recruitment	27
6.9 Early Withdrawal of Subjects	27
7 REGISTRATION PROCEDURES	29
7.1 CUMC Research Participant Registration	29
8 TREATMENT PLAN	31
8.1 Agent Administration.....	31
8.2 General Concomitant Medication and Supportive Care Guidelines.....	31
8.3 Duration of Therapy.....	33
8.4 Duration of Follow Up.....	34

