Nivolumab has demonstrated a manageable safety profile in > 8600 participants across all clinical trials. The most common AEs included fatigue, rash, pruritus, diarrhea, and nausea. The AE profile for nivolumab monotherapy does not appear to be dose dependent and appears to be similar across a range of solid tumors studied. This manageable toxicity profile makes nivolumab a suitable therapeutic option in this older participant population. Together the data suggest a positive benefit-risk potential, supporting a Phase 2 study to further assess the efficacy and safety of nivolumab in progressive or recurrent IDH mutant gliomas.

Rationale for Nivolumab Dose Selection

Nivolumab will be given 240 mg every 2 weeks (Q2W) IV for 8 cycles followed by 480 mg every 4 weeks (Q4W), for a total of 2 years of treatment duration or until progressive disease, unacceptable toxicity, or withdrawal of consent. The infusion duration for both dosing regimens will be 30 minutes.

The nivolumab dose of 240 mg Q2W was selected based on clinical data and modeling and simulation approaches using population pharmacokinetics (PPK) and exposure-response analyses of data from studies in multiple tumor types (melanoma, non-small-cell lung cancer [NSCLC], and renal cell carcinoma [RCC]) where body weight-normalized dosing (mg/kg) has been used. PPK analyses have shown that the PK of nivolumab is linear with proportional exposure over a dose range of 0.1 to 10 mg/kg, and no differences in PK across ethnicities and tumor types were observed. Nivolumab clearance and volume of distribution were found to increase as the body weight increases, but less than proportional with increasing weight, indicating that mg/kg dosing represents an over-adjustment for the effect of body weight on nivolumab PK.

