5 STUDY DESIGN

5.1 General Design

[figure not shown]
This is a Phase 2, open-label, single-arm study to estimate the safety and efficacy of nivolumab in participants with recurrent or progressive IDH mutated glioma after exposure to alkylating agents. Nivolumab 240 mg will be given every 2 weeks for 8 cycles. Beginning with Cycle 9, nivolumab 480 mg will be given every 4 weeks for a total therapy duration of 2 years, or until progressive disease, unacceptable toxicity, or withdrawal of consent. Nivolumab will be administered as a 30-minute infusion. A finite treatment duration with immune therapies in this participant population remains an area of ongoing research; therefore the treatment duration chosen was 2 years.

The study will further characterize safety and evaluate the antitumor activity of nivolumab in participants with recurrent IDH mutant glioma who progressed after or did not respond to alkylating agents.

The primary endpoint is ORR, and will be analyzed 6 months after the last participant's first treatment in the trial.

The study design schematic is presented in Figure 5.1-1.

Figure 5.1-1: Study design schematic

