9 DOSING DELAYS/DOSE MODIFICATIONS

Dose Modifications for Nivolumab

Dose modifications are not allowed for nivolumab.

Dose Delay Criteria for Nivolumab

Tumor assessments should continue per protocol schedule, even if dosing is delayed. Treatment delays will be recorded, but the total duration of therapy will be up to two years, regardless of the number of cycles. Nivolumab administration should be delayed for the following:

- Any Grade ≥ 2 non-skin, drug-related AE, with the following exception:
 - Grade 2 drug-related fatigue or laboratory abnormalities do not require a treatment delay
- Grade 2 drug-related creatinine, AST, ALT, or TBILI abnormalities
- Any Grade 3 skin, drug-related AE
- Any Grade 3 drug-related laboratory abnormality (excluding AST, ALT, or TBILI), with the following exceptions for lymphopenia or asymptomatic amylase or lipase:
 - Grade 3 lymphopenia does not require dose delay
 - Any Grade ≥ 3 drug-related amylase or lipase abnormality that is not associated with symptoms or clinical manifestations of pancreatitis does not require dose delay
- Any AE, laboratory abnormality, or intercurrent illness which, in the judgment of the investigator, warrants delaying the dose of study medication [L]
[SEP]

Participants who require delay of nivolumab should be re-evaluated weekly or more frequently if clinically indicated, and resume nivolumab dosing when re-treatment criteria are met.

Criteria to Resume Dosing for Nivolumab

Participants may resume treatment with study drug when the drug-related AE(s) resolve to Grade ≤ 1 or baseline value, with the following exceptions:

- Participants may resume treatment in the presence of Grade 2 fatigue.
- Participants who have not experienced a Grade 3 drug-related skin AE may resume treatment in the presence of Grade 2 skin toxicity.
- For participants with Grade 2 AST, ALT, or TBILI elevations, dosing may resume when laboratory values return to baseline and management with corticosteroids, if needed, is complete.
- Participants with combined Grade 2 AST/ALT AND TBILI values meeting discontinuation parameters should have treatment permanently discontinued.

Columbia University Medical Center
Herbert Irving Comprehensive Cancer Center
Version Date: January 30, 2024

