			no less than 12 days from the previous dose. For Q2W dosing cycles, participants may be dosed within a ± 2 day window. Beginning with Cycle 9, participants should receive Nivolumab at a dose of 480mg as a 30-minute infusion every 4 weeks (± 3 days) for a maximum 2 years of total treatment, or until PD, unacceptable toxicity, or withdrawal of consent.
Correlative Assessments			
Blood for Whole Exome Sequencing	X		Blood sample can be drawn on C1D1 or at anytime while the patient is on study, see laboratory manual for additional details
¹ All windows proposed are calendar days. Procedures must be done within 72h prior to dosing unless otherwise specified. Cycle duration is 2 weeks until 8 doses have been completed; subsequent cycles are 4 weeks in duration			

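### The 28-cycle allowance in Section 8.3 works out to 96 weeks, 8 weeks and 2 cycles short of the 2-year duration in the schema, 4.3 and 5.1, and it conflicts with Section 9

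*Combined protocol and SAP*

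**What the plan says.** Section 8.3 gives the duration as a number of cycles, for participants without adverse-event delays: "In the absence of treatment delays due to adverse events, treatment may continue for 28 cycles or until one of the following criteria applies". The footnote to Table 12.2 fixes the cycle length: "Cycle duration is 2 weeks until 8 doses have been completed; subsequent cycles are 4 weeks in duration". The dosing table in 8.1 agrees.

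Other places give the duration in calendar time, in two kinds of wording.

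- As a total. The schema has "Total treatment duration for 2 years or until PD, unacceptable toxicity, or withdrawal of consent"; 4.3 (dose rationale) has "for a total of 2 years of treatment duration or until progressive disease"; 5.1 has "for a total therapy duration of 2 years, or until progressive disease, unacceptable toxicity, or withdrawal of consent" and adds that two years was the duration chosen.
- As a ceiling. The synopsis row on duration of administration gives two years as an upper limit, and Table 12.2 has "for a maximum 2 years of total treatment".

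Section 9, after saying that delays are recorded, states that "the total duration of therapy will be up to two years, regardless of the number of cycles". Sections 8.1 and 11.2 give neither years nor a cycle count; they run to the end of the study. Nothing in the document equates 28 cycles with 2 years, defines a year as 48 weeks, or says which section prevails.

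**The concern.** A cycle count and a calendar duration can both stand in a protocol if one converts into the other. Here they do not convert. A site with an on-schedule participant reaching week 96 finds one section that ends treatment there and others that describe two years. A dose given at week 96 or week 100 is then either per protocol or a deviation, depending on the section consulted, and the study runs at three sites.

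The end of treatment also drives later events. The off-drug visits X01 and X02 are timed from the last dose, and Table 12.2 ties the 8-weekly MRI schedule to being on treatment. The participants concerned are those still progression-free and on drug near two years, who supply the late part of the PFS and duration-of-response data.

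**Working it through.** **Inputs.** Cycle allowance: 28 (8.3). Cycle length: 2 weeks for cycles 1–8, 4 weeks from cycle 9 (8.1, Table 12.2). Total duration: 2 years (schema, 4.3, 5.1), taken as 104 weeks. X01 is 35 days after the last dose and X02 is 80 days after X01 (Table 12.3 footnote). MRI is every 8 weeks from C1D1 (Table 12.2).

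**Length of 28 cycles.** 8 × 2 + (28 − 8) × 4 = 16 + 80 = 96 weeks = 672 days. 672 / 365.25 = 1.84 years, or 22.1 months. The 28th dose falls at 16 + 19 × 4 = week 92.

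**Cycles in 2 years.** 8 + (104 − 16) / 4 = 8 + 22 = 30 full cycles, with cycle 29 starting at week 96 and cycle 30 at week 100. The shortfall is 104 − 96 = 8 weeks and 30 − 28 = 2 cycles. Using 730 or 731 days instead of 728 still gives 30 completed cycles, although a 31st dose would then fall nominally just inside the limit, on day 728.

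**Can 28 be reproduced?** Only if a month is counted as 4 weeks: 16 weeks / 4 = 4 months, plus 20 four-week cycles, gives 24 months. Section 4.3 does describe the 8 two-week cycles as 4 months, so this may be where 28 came from. That is an inference; the protocol states no such convention.

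**Sections 8.3 and 9 read together.** Suppose 8.3 caps undelayed participants and Section 9 lets delayed ones run to week 104. With a total delay of d weeks, the full cycles that fit by week 104 are 8 + (104 − 16 − d) / 4, rounded down.

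| Total delay (weeks) | Limit applied | Full cycles | Latest end of treatment |
|---|---|---|---|
| 0 | 8.3 | 28 | week 96 |
| 2 or 4 | Section 9 | 29 | week 104 |
| 6 or 8 | Section 9 | 28 | week 104 |
| 12 | Section 9 | 27 | week 104 |

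On this reading a participant delayed by 2 to 4 weeks can complete one more cycle than a participant who was never delayed. With 6 or 8 weeks of delay the number of full cycles is the same and only the calendar end differs. If Section 9 governs everyone, the undelayed participant can complete 30 cycles and this asymmetry disappears.

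**Visits and scans.** X02 follows the last dose by 35 + 80 = 115 days = 16.4 weeks. It falls at 92 + 16.4 = week 108.4 when the last dose is cycle 28, or at 100 + 16.4 = week 116.4 when it is cycle 30. Late scans on the 8-week grid fall at weeks 88, 96 and 104. The week-104 scan is the one whose status changes; week 96 is a boundary case.

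**Primary analysis.** ORR is analysed 6 months after the last participant's first treatment (5.1). At the planned 3 per month (15.2), 37 participants take 37 / 3 = 12.3 months, so the analysis falls about 18.3 months after the first participant starts. Dose 28 falls at 92 × 7 = 644 days, and 644 / 30.4375 = 21.2 months. At planned accrual nobody would have reached it by then.

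**The case against.** The strongest defence is that 8.3 is permissive, saying treatment may continue, and that Section 9 settles the matter by putting calendar time above the cycle count. On that reading there is one limit for everyone and 8.3 merely carries a stale number. This is a fair reading, but it confirms that 8.3 needs correction, and no passage says that Section 9 overrides it.

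A reader might infer several stronger things that the documents do not support.

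- *That every other section says 2 years.* Sections 8.1 and 11.2 give no numerical duration.
- *That 96 weeks breaks every two-year statement.* It is within the ceilings in the synopsis row and Table 12.2, and within Section 9's upper limit. The clash is with the total-duration wording in the schema, 4.3 and 5.1, and with Section 9's rejection of a cycle count.
- *That undelayed participants are certainly stopped earlier than delayed ones.* This requires 8.3 to be a hard cap and Section 9 to apply only where there were delays. The text allows that reading but does not compel it.
- *That PFS or duration of response is biased.* No effect on either estimate can be calculated from the documents, which do not say how many of the 37 participants would still be on drug near week 92. After treatment, RANO assessments must still be completed and documented until progression or new therapy (5.6, Table 12.3). The schema runs 8-weekly assessments for up to 2 years without tying them to treatment.

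**Conclusion.** The discrepancy is real and exact: 96 weeks against 104, or 28 cycles against 30. It rests on the protocol's own nominal cycle lengths and on counting 2 years as 104 weeks. On either reading of Section 9 the text has to change: one gives different stopping points to delayed and undelayed participants, and the other leaves a wrong count in 8.3.

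The consequence is modest. It reaches only participants still on drug near week 92. For them the end of treatment moves by up to 8 weeks and 2 doses, the off-drug visits move by the same 8 weeks, and about one scan changes between protocol timing and local standard of care. The test of ORR does not use treatment duration, and at planned accrual it is done before anyone reaches the 28th dose, so the primary result is essentially unaffected. The reason to act is that this figure governs when study drug and on-treatment scans stop, and sites can apply it differently.

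**What to change.** Reconcile 8.3 with the synopsis and schema, 4.3, 5.1, Section 9 and Table 12.2. State one limit, in calendar time or in cycles, and make any cycle count quoted beside it agree with the stated duration at the protocol's cycle lengths. Say whether the limit is the same for participants with and without delays. Align the end of the 8-weekly scan schedule in Table 12.2 with that limit, and with the schema, which does not tie scans to treatment. Which limit is intended is for the sponsor to decide; this review takes no position on it.

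The cost is a short text amendment. It adds no procedures and changes neither the sample size nor the analysis.
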